APPENDIX 1 – MEN Count Study Protocol

Background

The Making Employment Needs (MEN) Count intervention was originally developed and pilot tested using a community-based participatory research approach via funding from the National Institute of Mental Health Grant R21MH085614 grant in Boston, MA.¹ The MEN Count study aimed to determine the efficacy of the MEN Count intervention in terms of its impact on incident STI and heterosexual risk for HIV (i.e., unprotected sex with multiple female sex partners in the past 90 days) among Black heterosexual men (n=454). The two armed quasi-experimental evaluation study enrolled participants in either the MEN Count counseling intervention or an attention comparison group focused on stress reduction. Participants were assessed via survey and HIV/STI testing at baseline and 6- and 12-month follow-ups to test the hypotheses that MEN Count participants, relative to attention comparison participants, would: (a) report a reduction in sexual risk, as measured by unprotected sex episodes and transactional sex in the past 90 days at each follow-up; and (b) have lower incident STI across the follow-up period. This study also aimed to examine the MEN Count intervention's impact on social determinants of health outcomes including employment and homelessness, as well as the intervention's impact on expected mediators (i.e. masculinity ideologies, social-structural factors, and social-cognitive factors) of behavior change, and to explore whether these factors mediated the relationship between the intervention and study outcomes.

Methods/Design

Setting

This study primarily took place in a local STI clinic in Washington D.C.

Curriculum Development

After pilot testing, prompts were embedded into the curriculum to identify checkpoints when MEN Count case managers (CMs) should provide referrals for HIV/STI testing. Prompts were also added to help CMs inquire about the participant's employment situation, potential violence in relationships, HIV/STI testing history and managing HIV risk.

MEN Count Peer Counselors

MEN Count CMs received professional development and training opportunities related to: stress management, anger management, DC resource referrals, mental health status assessment, substance abuse or addiction detection, sensitivity training about gender and sexual identity and LGBT diversity, healthy masculinity, and case note writing.

Pilot Testing

To ensure high quality implementation in the clinic setting prior to the RCT, the MEN Count intervention and evaluation measures were piloted with 10 eligible Black men recruited from a community-based organization and stakeholder referrals in order to provide qualitative and quantitative feedback on the

¹ Raj A, Dasgupta A, Goldson I, Lafontant D, Freeman E, Silverman JG. Pilot evaluation of the Making Employment Needs [MEN] count intervention: addressing behavioral and structural HIV risks in heterosexual black men. *AIDS Care*. 2014;26(2):152-159.

[figure not shown]
intervention and protocol procedures. Pilot participants completed the baseline survey, MEN Count intervention sessions given over the course of two months, follow-up survey and a brief interview about their response to the program. Feedback from the pilot was used to tailor the intervention to the clinic setting. Participants received \$35 cash at baseline and \$25 for their feedback interview.

Intervention

For the MEN Count study, participants received \$30 cash at baseline and an additional \$40 at six-month follow up and \$50 at 12-month follow up. Clinic and study staff provided standard of care HIV/STI counseling and testing, including support for follow-up and linkage to care or treatment if a participant received a positive HIV/STI test result. To document intervention participants' understanding of how the intervention affected their HIV/STI risk and protective behaviors, in-depth interviews were conducted with a subsample of participants (10%) at follow-up, and with all study CMs to assess their perspectives on program implementation and impact. Participants received a \$50 cash incentive for their participation in the 60-90 minute interview.

Each session included: 1) Personalized employment, housing stability and sexual risk assessments; 2) Guided examination of why identified risks (e.g., multiple sex partners, non-condom use) occur, considering theory-supported risk factors including traditional masculinity ideologies, substance use, mental health, and low HIV/STI knowledge and risk perceptions; 3) Identification of social or health service (e.g., substance abuse treatment and mental health services) referrals or known job opportunities to reduce concurrent sexual partnerships affected by these concerns; 4) Support for maintenance in stable job or housing situations when frustrations about these occur; and 5) Problem solving via an action plan of concrete steps the client could take to reduce non-condom sex practices and to stabilize their housing and employment; and recognition/positive reinforcement of enactment of action plans (Sessions 2&3).

Figure 1: Structure and Timing of MEN Count Intervention Delivery over 60-90 Days

"Washington D.C., 2014-2017"

Attention-Comparison Condition. The stress education and reduction program offered to control condition participants followed the same 60-90 day 3-session structure of the MEN Count intervention. This program focused on how to reduce stress and tension via diet, exercise, and effective

communication. Excluded from focus were issues of HIV/STIs, substance use, and masculinity ideologies. The program did retain linkage to job placement and housing resource provision, however.

Eligibility

At recruitment, staff screened potential study participants to assess eligibility. Eligible participants self-identified as Black or African American men, aged 18 years or older and English fluent; reported sex with two or more women in the past 12 months AND unprotected vaginal sex in the past 12 months; reported homelessness in the past 6 months (at least one night in shelter or on the streets) OR current unemployment (currently having no legal employment for money); were willing to participate in the MEN Count program, complete surveys, and be tested for STIs; and could provide contact information for themselves and two other individuals through whom we could reach them. Exclusion criteria were outlined on the basis of their potential impact on study participation or intervention testing effects. Participants were excluded from the study if they: planned to leave Washington D.C., Maryland, or Virginia in the next 6 months, were cognitively impaired (based on Folstein Mini-Mental Exam at recruitment or baseline testing), and/or had self-reported health status that prohibited them from participating in the program.

Methods for Data Collection.

Quantitative. Study staff used mobile tablet surveys to collect detailed data on participants' demographics, risk behaviors, HIV/STI risk profile, and HIV/STI knowledge, attitudes and risk perceptions. Trained research staff conducted surveys in a private room at the study site. Study participants could opt to enter their survey responses directly into the tablet survey system in real-time on their own, or study staff could enter responses. Study staff uploaded completed surveys securely and directly to a secure server system. For STI testing, researchers collaborated with a D.C. area STI clinic and established a confidentiality agreement to share participant HIV/STI test results for only those participants that enrolled in the study and consented to have their HIV/STI results shared for the purposes of this study. The STI clinic shared participant HIV/STI test results with the program manager securely on a monthly basis. In order to link baseline survey and follow-up data, surveyors uploaded research ID-assigned (i.e., de-identified) test result data to the database.

Qualitative. Qualitative interviews lasted between 45 and 60 minutes were conducted by the D.C.-based project director, a Black woman, and a Black male graduate research assistant either in-person or by phone. The semi-structured interview guide included questions designed to elicit feedback about participants' experiences with the program, including what they liked and did not like about the program, the perceived effectiveness of the program in terms of facilitating housing and employment, and ways to improve the program.

Data Management. All data collected for this study were assigned a unique identifier at each time point to facilitate linkage of longitudinal data over time. The web-based tracking system to which data were uploaded included only data with research ID numbers as identifiers.

Data Safety and Monitoring. A data safety and monitoring board was created to assure adherence to safety protocols intended to protect participants and monitor data protection efforts.

IRB

The MEN Count protocol and study materials were approved by the Institutional Review Boards at The George Washington University, The University of California San Diego, and the District of Columbia Department of Health.

Power Calculation

Power calculations were conducted based on an intended sample size of 504 and assumed two-sided tests with a 0.05 type I error rate. Power calculations were focused on reduction of STI incidence as it was the more conservative analysis. A 25% attrition rate, assumed to be high and to be expected for this population, resulted in an assumed $n=378$ participants at follow-up. Power calculations were based on a two-sided Poisson regression of a dependent variable of counts (i.e. number of incident STI cases) on a binary independent variable (treatment group) with proportion of 0.50 (i.e. 189 participants) in each group adjusting for age, marital status, employment and homelessness (assuming the estimated R-squared of the independent variable regressed on these four covariates is 0.04). The estimates used for these power calculations were based on a recent HIV intervention study with young Black heterosexual men recruited from STI clinics. The STI clinic study found that comparison group participants were almost 3 times as likely to be STI-infected at follow-up relative to intervention participants. MEN Count pilot data were too small to see intervention impact on STI but did document a baseline STI rate of 13% in this target population. Using these data, the proposed sample size of $n=378$ would have at least 80% power to detect a rate ratio (Group 1/Group 2) of at least 0.28 (intervention incidence rate=2%), 0.31 (intervention incidence rate=2.5%), 0.34 (intervention incidence rate=3%) or 0.36 (intervention incidence rate=3.6%), respectively, assuming the 1-year cumulative STI incidence rate in the Comparison Group is 7%, 8%, 9%, or 10%.

Though difference-in-difference multivariate regression models were used to assess outcomes (see below), analyses were also performed as outlined by power calculation assumptions (e.g. utilizing Poisson models and specified covariates) and also found null results for the incident STI outcome.

Analytic Plan

Outcome analyses were designed to focus on four outcomes of interest (defined in greater detail below): incident non-viral STI, sexual risk, homelessness, and unemployment. The primary comparison of outcomes by treatment group was assessed using mixed-effects multivariate regression models (logistic and multinomial, dependent on outcome) with random effects on individual to account for repeated measurements over time. The treatment effect was evaluated via a time-by-treatment arm interaction term. A categorical time effect was used. This treatment effect can be interpreted as the individual-level effect of the intervention, and this analytic strategy addresses problems of attrition, missing data, variable timing of subject visits and other possible unintended violations of design common to longitudinal studies. Demographic covariates were included in all outcome models if they were significantly associated with treatment group at baseline in bivariate chi-squared tests at $p<0.20$. For each outcome, additional potential covariates were included if they were associated with the given outcome in bivariate chi-squared tests at $p<0.05$. Dose effects of the MEN Count intervention were evaluated using a similar analytic strategy, examining a time-by-dose interaction instead of time-by-study arm.

Outcome Definitions

Pursuant to previous HIV prevention research with Black heterosexual men that used ordinal index of sexual risk categorization, sexual risk was categorized as very low, low, medium, and high.² Very low sexual risk was defined as having one partner and consistent condom use. Low sexual risk was defined as having multiple partners and consistent condom use OR one partner and no/inconsistent condom use. Medium sexual risk was defined as having multiple partners, no/inconsistent condom use and not participating in transactional sex. High risk was defined as having multiple partners, no/inconsistent condom use, and participating in transactional sex. Participants reporting sex with men in the prior 90 days (n=20) or who reported that they themselves or (one of) their partner(s) was HIV-positive (n=31) were excluded from the sexual risk outcome analysis given the known differential HIV risk profile for these subpopulations and small numbers of participants in each.

Where data for the direct item on number of female sex partners was missing (n=1) or inconsistent with other partner-related responses (n=36 reported both main and non-main partners in this time frame, but only 1 partner on the direct item), responses to questions about having had sex with a main and other partner(s) were used. Consistency of condom use was determined based on the ratio of the number of condom protected vaginal or anal sex acts to the total number of vaginal or anal sex acts in the past 90 days. Consistent condom use was categorized as yes (number of acts with condom equal to total number of acts) or no (number of sex acts with condom use less than total number of acts). Transactional sex was defined as answering yes to any of the following items: having had sex for money, having given money in exchange for sex, having had sex for a place to stay, having had sex for drugs, or having given drugs in exchange for sex in the past 90 days.

Homelessness was characterized as at least one night of homelessness in the past 90 days. Participants were categorized as having experienced homelessness if they answered 'homeless on the streets' or 'homeless in a shelter' in response to the question 'what best describes your living situation in the past 90 days?' or if they had a non-zero response to either of two questions asking how many of the previous 90 days the participant was homeless on the streets or homeless in a shelter.

Employment was assessed via a single item asking the participant's current employment status. Participants could indicate that they were not employed, were not legally employed but had a job with income, or were legally employed full-time or part-time. Participants reporting that they were unemployed or illegally employed were categorized as unemployed.

Process Evaluation

Quality assurance and process evaluation efforts aimed to ensure a high quality program via collection of data through eligibility screeners, surveys, and brief qualitative interviews regarding program feedback. Process evaluation determined fidelity to the intervention as well as confirmed and reviewed intervention sessions delivery. A licensed clinical social worker (LCSW) on the research team provided clinical supervision to the peer case managers delivering the MEN Count intervention and control

² Bowleg, L., Burkholder, G. J., Massie, J. S., Wahome, R., Teti, M., Malebranche, D. J., & Tschann, J. M. (2013). Racial discrimination, social support, and sexual HIV risk among Black heterosexual men. *AIDS and Behavior, 17*, 407-418. doi:10.1007/s10461-012-0179-0

condition. Group phone meetings were held monthly (more frequently, if needed) with the case managers, along with the case manager's project manager. Initially, sessions took place every two weeks when case managers were new. As the study progressed and client sessions ended, clinical supervision session frequency diminished. Clinical supervision check-ins involved discussion of the following topics. First, any crisis "SHADE" (Suicide, Homicide, Abuse, Drugs, Eating/Health issues) situations shared with case managers since the last clinical supervision check-in were prioritized. Discussion was then held on intervention delivery (as scripted, in 1-hr period) as well as any challenges with regard to covering the session material. During this time, the LCSW shared insights gleaned from listening to the case managers' recorded sessions with clients. The LCSW provided feedback and recommendations about how to strengthen case manager sessions, ways to include intervention material, and suggested case management resources and treatment plans. Finally, the LCSW and program manager discussed any questions or challenges from case managers regarding recruitment or follow up and assisted with developing solutions (such as modifications to follow-up surveys, transportation vouchers for participants to attend sessions, and more frequent check-ins between sessions).

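### With 378 men and R-squared 0.04, the planned Poisson test of incident STI has about 67-68% power (likelihood ratio) or 57-64% (Wald), not at least 80%, in all four scenarios

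*Combined protocol and SAP*

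**What the plan says.** All the inputs are in the Power Calculation section of the combined protocol and SAP.

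- Sample and error rate: "Power calculations were conducted based on an intended sample size of 504 and assumed two-sided tests with a 0.05 type I error rate". Attrition of 25% leaves 378 men, 189 per group.
- Model: "a two-sided Poisson regression of a dependent variable of counts (i.e. number of incident STI cases) on a binary independent variable (treatment group"), adjusted for age, marital status, employment and homelessness.
- Covariate adjustment: "assuming the estimated R-squared of the independent variable regressed on these four covariates is 0.04".
- Comparison group: "assuming the 1-year cumulative STI incidence rate in the Comparison Group is 7%, 8%, 9%, or 10"%.
- Claim: this sample "would have at least 80% power to detect a rate ratio (Group 1/Group 2) of at least 0.28 (intervention incidence rate=2"%), with ratios of 0.31, 0.34 and 0.36 for the other three scenarios (intervention rates 2.5%, 3% and 3.6%).

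No formula, software or type of test (Wald, score or likelihood ratio) is named. The next paragraph says that analyses following the power assumptions were also run, "utilizing Poisson models and specified covariates) and also found null results for the incident STI outcome". The primary comparison in the Analytic Plan is a different model: "mixed-effects multivariate regression models (logistic and multinomial, dependent on outcome"). The Background gives the study population as "among Black heterosexual men (n=454").

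**The concern.** Few events are expected under these inputs. At 7% incidence and a ratio of 0.28 there would be about 13 cases in one arm and 4 in the other. Approximations to Poisson power can be well off at such counts when the assumed effect is this large, so the stated 80% needed a direct check.

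At stake is how a null result is read. The text moves straight from the power claim to a null incident-STI finding from the same model. It does not itself argue that the null rests on 80% power, but a reader will set the two side by side and take the chance of missing a roughly threefold effect to be at most 20%.

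**Working it through.** **Inputs (all from Power Calculation).** Two-sided 5%, so z = 1.960; n = 504 × 0.75 = 378; 189 per arm; R² = 0.04, which scales the information by 0.96; comparison rate λ = 0.07, 0.08, 0.09, 0.10; rate ratio RR = 0.28, 0.31, 0.34, 0.36. As in the plan, one-year cumulative incidence is used as the Poisson mean per man.

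**Step 1. Expected cases**, 189λ and 189λ·RR: 13.2 + 3.7, 15.1 + 4.7, 17.0 + 5.8, 18.9 + 6.8. The totals are about 17, 20, 23 and 26.

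**Step 2. Reproducing the plan's figure.** A standard Poisson-regression formula for a binary covariate with proportion p = 0.5 (the Signorini formula) is

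n = [z·√V0 + z_power·√V1]² / [λ·(ln RR)²·(1 − R²)],

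with V0 = 1/(1−p) + 1/p = 4 and V1 = 1/(1−p) + 1/(p·RR). This V0 sets both arms at the comparison rate.

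For scenario 1:
- V1 = 2 + 2/0.28 = 9.143, √V1 = 3.024, |ln 0.28| = 1.273.
- R² = 0: √(378 × 0.07) × 1.273 = 6.548; (6.548 − 1.960 × 2)/3.024 = 0.869, so power is 80.8%.
- R² = 0.04: √(378 × 0.07 × 0.96) × 1.273 = 6.416; (6.416 − 3.920)/3.024 = 0.825, so power is 79.5%.

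The formula therefore comes close to the stated 80%. At R² = 0 its 80% ratios are 0.286, 0.315, 0.341 and 0.363; cut to two decimals, these are the four printed values. At R² = 0.04 they are 0.277, 0.306, 0.332 and 0.355 (0.3545 before rounding), and only the first two match on rounding. The sample it needs for 80% at the printed ratios is 369, 370, 377 and 373 at R² = 0 (all within 378), but 384, 385, 393 and 388 at R² = 0.04 (all above 378).

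**Step 3. Same formula with the null variance at the pooled rate.** V0 = 4/[(1 + RR)/2]. In scenario 1 this is 6.25, so (6.416 − 1.960 × 2.5)/3.024 = 0.501 and power is 69.2%.

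**Step 4. Direct power.** I enumerated two independent Poisson counts with means 0.96 × 189 × λ and 0.96 × 189 × λ·RR, and summed the probability of every pair that each test declares significant. For Wald, a zero count in either arm is treated as not significant.

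| Power, % | 7%, 0.28 | 8%, 0.31 | 9%, 0.34 | 10%, 0.36 |
|---|---|---|---|---|
| Formula, comparison-rate null, R² = 0 | 80.8 | 80.7 | 80.1 | 80.5 |
| Same, R² = 0.04 | 79.5 | 79.5 | 78.8 | 79.2 |
| Formula, pooled null, R² = 0.04 | 69.2 | 69.3 | 68.8 | 69.5 |
| Direct, likelihood ratio | 67.4 | 67.2 | 66.8 | 67.8 |
| Direct, score | 64.3 | 66.0 | 66.5 | 67.7 |
| Direct, Wald | 57.0 | 61.0 | 62.6 | 64.4 |

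Reading down to the likelihood-ratio row: R² costs about 1 point, the null-variance choice about 10, and the small counts about 2.

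**Step 5. Ratios that do have 80% power** at n = 378 and R² = 0.04 by likelihood ratio: 0.21, 0.24, 0.26 and 0.29. By Wald, no ratio reaches 80% at 7% or 8% incidence (maximum 66.7% and 76.4%).

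**Step 6. Robustness.**
- Type I error of the likelihood-ratio test here is 5.2-5.3%, so its power is not held down by conservatism.
- R² = 0: likelihood ratio 68.6-69.6%.
- Printed intervention rates in place of the ratios: likelihood ratio 66.4-68.0%.
- Each man infected yes or no (two-proportion likelihood ratio): 69.5-71.5% at 181 per arm (0.96 × 189), 71.4-73.3% at 189 per arm.
- 4,000 simulated Poisson regressions per scenario with four covariates: likelihood ratio 65.7, 66.4, 66.1, 67.4%; Wald 56.4, 60.8, 61.8, 63.8% (Monte Carlo standard error about 0.7-0.8 points).
- All 454 men analysed, Poisson likelihood ratio, R² = 0.04: 74.5-75.6%. All 504: 78.7-79.8%.

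**The case against.** The best defence is that the 80% is no slip of arithmetic. A recognised formula that takes exactly the listed inputs gives 78.8-79.5%, within about 1 point of the claim, and since the plan names no test, no named test was miscalculated. This explains where the figure probably came from, and it makes the shortfall a matter of approximation rather than careless calculation. It does not make the statement true: the plan asserts a property of the trial, not the output of a formula, and none of the tests tried has that property. Even on the favourable formula, all four scenarios fall below 80% at the stated R-squared.

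Some narrower objections stand.
- Whether R-squared 0.04 was left out cannot be settled from the document. The match depends on cutting rather than rounding decimals, and the matter is worth about 1 point.
- The results for 454 and 504 men hold only for the Poisson likelihood ratio at R-squared 0.04. With 504 men, R-squared 0 gives 80.3-81.3%, and the infected-yes-or-no calculation gives 79.5-82.3%. With 454 men, the latter gives 75.1-78.1%.
- The miss probabilities apply at the planned sample size and assumed incidence. The document gives neither the number analysed nor the observed incidence.
- The null at issue comes from a supplementary analysis; none of these figures describes the mixed-effects primary model.
- The estimate and interval may already appear in a results report not seen here.

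**Conclusion.** The concern holds. For the Poisson analysis as described, power at the listed ratios is about 67-68% by likelihood ratio, the most favourable Poisson test tried, and 57-64% by Wald. The overstatement is about 12-13 points and 16-23 points respectively against 80%. The chance of missing an effect of the listed size is 32-33% (likelihood ratio) or 36-43% (Wald), not at most 20%.

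This rests on the plan's own inputs and on its use of cumulative incidence as a Poisson mean; relaxing that, or setting R-squared to 0, still leaves every scenario below 80% at n = 378. That the authors used a formula with comparison-rate null variance is inferred from the match, not documented. The error should be fixed, because a headline design figure stands next to a null result for the same outcome, but it changes neither the sample nor the analyses.

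**What to change.** Keep the sentence as the planning record and add a note such as:

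> At n=378, two-sided 5% and R-squared 0.04, direct calculation gives power of about 67-68% (likelihood-ratio test) or 57-64% (Wald test) at the listed ratios; 80% power by likelihood ratio needs ratios of about 0.21, 0.24, 0.26 and 0.29. These figures apply to the Poisson analysis, not to the mixed-effects primary model.

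Also:
- State the formula or software used, and confirm from the power-calculation record whether R-squared 0.04 was applied.
- Give, or point to, the estimate and confidence interval of the Poisson STI analysis, and read the null from them rather than against 80% power.
- Optionally, note that with all 454 enrolled men analysed the Poisson likelihood-ratio power at R-squared 0.04 would be about 75%.

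The cost is a few lines of text and a look at the original record. The stated power becomes less favourable; no participants are added and no analysis changes.

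### The power stated for incident STI belongs to a single pooled arm term; the primary time-by-arm model splits about 4–7 expected intervention-arm infections over two visits and has far less power

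*Combined protocol and SAP*

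**What the plan says.** All references are to Appendix 1 of the combined protocol and SAP.

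**Power Calculation.** "Power calculations were conducted based on an intended sample size of 504", and it "assumed two-sided tests with a 0.05 type I error rate". On attrition: "A 25% attrition rate, assumed to be high and to be expected for this population, resulted in an assumed $n=378$ participants at follow-up". The model is a Poisson regression of infection counts on one binary arm variable "with proportion of 0.50 (i.e. 189 participants) in each group", adjusted for age, marital status, employment and homelessness, "assuming the estimated R-squared of the independent variable regressed on these four covariates is 0.04". Power of at least 80% is given for rate ratios of 0.28, 0.31, 0.34 and 0.36 (intervention incidence 2%, 2.5%, 3% and 3.6%), "assuming the 1-year cumulative STI incidence rate in the Comparison Group is 7%, 8%, 9%, or 10" per cent. The section also reports that Poisson analyses on these assumptions were run in addition to the difference-in-difference models, and were null for incident STI.

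**Analytic Plan.** The primary comparison for all four outcomes, incident non-viral STI among them, uses "mixed-effects multivariate regression models (logistic and multinomial, dependent on outcome) with random effects on individual". Time is categorical, and "The treatment effect was evaluated via a time-by-treatment arm interaction term".

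**Background.** Testing was at baseline, 6 and 12 months. The STI hypothesis concerns incidence over follow-up as a whole.

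The text names no test (Wald, likelihood ratio or other), no sparse-data method and no single contrast across the two interaction terms. Outcome Definitions covers sexual risk, homelessness and employment, but gives no definition of incident STI or its coding by visit.

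**The concern.** The trial was sized on STI incidence, but the stated power describes a different analysis from the primary one. The power model uses every follow-up infection for one arm contrast. The primary model divides the same few infections between two visit-specific interaction terms and adds the sampling variance of the baseline comparison.

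If the intervention arm has no infection at a visit, the maximum-likelihood estimate of that visit's interaction runs to minus infinity. Its Wald standard error then means nothing, and even near-empty cells make the Wald statistic a poor guide. The problem is worst when the intervention works as planned. At stake is the reading of a null result: with this primary model it says much less about the planned effect than the 80% figure suggests.

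**Working it through.** **Inputs.** From the Power Calculation: two-sided 0.05; n = 378, 189 per arm; R-squared 0.04; comparison incidence 7–10%; intervention incidence 2–3.6%; pilot baseline STI rate 13%. From the Background: visits at baseline, 6 and 12 months. Assumptions of this check: infections split equally over the two follow-up visits, 13% positive in both arms at baseline, and (for the closed-form results) no within-man correlation.

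**1. The plan's figure.** The standard Poisson-regression formula with a binary covariate is

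z_power = [√(N(1−R²)·λ_C·(ln RR)²) − 1.96·√4] / √(2 + 2/RR).

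First scenario: N(1−R²) = 378 × 0.96 = 362.88 and (ln 0.28)² = 1.620. Then √(362.88 × 0.07 × 1.620) = 6.416, and (6.416 − 3.920)/√9.143 = 0.825, which is 79.5% power. The other scenarios give 79.5%, 78.8% and 79.2%. The stated figure is reproduced to within rounding.

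**2. Expected infections.** Intervention arm, whole year: 189 × p. Per visit: 189 × p/2.

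**3. Empty cells.** The chance of no infection at one visit is q = (1 − p/2)^189. At least one visit empty: 1 − (1 − q)². Both empty: q². For p = 2%, q = 0.99^189 = 0.150, giving 27.7% and 2.2%.

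**4. Power at the planned effect.** The joint Wald test of the two interaction terms was simulated 200,000 times per scenario and the likelihood-ratio (LR) test 40,000 times. The cumulative contrast is an unadjusted logistic LR test of infected during follow-up, by exact enumeration of the two binomials.

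| Comparison / intervention | Intervention infections: year (per visit) | ≥1 visit empty | Both empty | 2-df Wald | 2-df LR | One cumulative contrast, LR |
|---|---|---|---|---|---|---|
| 7% / 2% | 3.8 (1.9) | 27.7% | 2.2% | 13.8% | 46.5% | 70.4% |
| 8% / 2.5% | 4.7 (2.4) | 17.7% | 0.9% | 19.2% | 45.8% | 71.8% |
| 9% / 3% | 5.7 (2.8) | 11.2% | 0.3% | 24.1% | 44.7% | 73.4% |
| 10% / 3.6% | 6.8 (3.4) | 6.4% | 0.1% | 27.2% | 43.0% | 73.3% |

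Random-intercept fits (400 trials per scenario, intercept SD 0.5 or 1) scatter around these values. Wald gives 12–15% in the first scenario and 26–31% in the last; LR gives 44.5–49% and 43–45%. I read the results as about 14–28% for Wald and 43–49% for LR.

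**5. Where the power goes.** A Wald test of one cumulative follow-up contrast has 59–69%. A one-degree-of-freedom difference-in-difference on cumulative incidence has 48–52% (Wald). Splitting by visit then brings the joint Wald test to 14–27%. Empty cells are not the whole cause: in trials without one, joint Wald power is still only about 18–28%. In trials with one, Wald rejects in 3–8%, while LR rejects in most (84–97% in the random-intercept fits).

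**6. Sensitivity.** A 60/40 split over visits gives at least one empty cell in 8–30% of trials. With the 454 men enrolled and 25% attrition (454 × 0.75 / 2 ≈ 170 per arm) the range is 9–33%. With no effect and both arms at 7–10%, an empty cell in either arm occurs in at most 0.5% of trials.

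**The case against.** **No Wald test is specified.** This stands. A reader might infer that the primary analysis used Wald tests and so lost half or more of its power. The documents do not say which test was used. Against an LR test of the same terms, the simulated loss is below half in some scenarios: one set of fits gave 28% against 45% and 31% against 45% in the last two. The shortfall from 80% does not need the Wald assumption, since LR reaches only 43–49%.

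**The model still gives an estimate.** This largely stands. An empty visit makes one of the two interaction terms infinite, and the other remains estimable. Both are lost in only 0.1–2.2% of trials.

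**The random intercept can be estimated.** A reader might count only men positive at both follow-ups (0.25–0.53 expected under independence) and conclude that it cannot. That leaves out the baseline visit. About 2.4–3.7 men would be positive at two or more of the three visits under independence: sparse, but not nothing.

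**A pooled Poisson analysis was also run and was null.** This is a real mitigation, because it does not split infections by visit. It is not the primary comparison, however, and no test or interval method is given for it. Simulated unadjusted power for a pooled Poisson contrast is 59–67% (Wald) or 68–70% (LR), so part of the gap from 80% lies in the large-sample formula and not in the interaction model.

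**Incident STI may have been analysed as one cumulative outcome.** The hypothesis in the Background allows this, and the infinite-estimate problem would then largely disappear. The repeated-measures description in the Analytic Plan supports the visit-level reading, and the available definitions do not settle it.

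**The text is retrospective.** A change of primary model now is made with the result known. That limits how the fix may be presented, but does not remove the mismatch.

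**Conclusion.** The concern holds in this form: the primary model described for incident STI does not have the power that the Power Calculation states. At the planned effect it has about 14–28% by joint Wald test or 43–49% by LR, against a stated 80%, and at least one interaction estimate is infinite in about 6–28% of trials. One cumulative arm contrast tested by LR has about 70–73%. Most of the gain comes from the change of contrast, and less from LR or Firth estimation alone.

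These figures rest on the planning alternative, an equal split over visits, 13% positive at baseline and the visit-level reading of the outcome. They do not show that a true effect was missed. The documents give no observed STI counts, the pooled analysis was also null, and under no effect empty cells are rare.

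**What to change.** For incident STI:

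- Define one infected-during-follow-up indicator per man and make its arm contrast the primary comparison. Adjust for baseline STI status and the four covariates of the Power Calculation.
- Test the arm effect by likelihood ratio. Report a Firth-penalised estimate with a profile-likelihood 95% confidence interval.
- Tabulate infections by arm and visit.
- Show the interaction model as specified alongside, and state which test it used.
- Label the change as a re-analysis made after the results were known.
- Do not attribute the stated 80% power to the interaction model.

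Keep the mixed models for the common outcomes.

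**Cost.** No new data, a few lines of code and revised text. Firth estimation shrinks the estimate slightly. The unadjusted LR test is marginally liberal: the enumeration in step 4, with both arms at the comparison rate, gives type I error of 5.3–5.6%. Power stays below 80%, and disclosure does not make a post hoc change of primary analysis equivalent to a prespecified one.
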